**Promoting Follow-Up Care Self-Management for Adolescent and Young Adult (AYA) Childhood Cancer Survivors**

[name], MPH

**LIST OF ABBREVIATIONS**

AYA	Adolescent and Young Adult
CINJ	Cancer Institute of New Jersey
LITE	Long-term, Information, Treatment effects, and Evaluation program
IRB	Institutional Review Board
NCI	National Cancer Institute
NIH	National Institutes of Health
PI	Principal Investigator
CCSS	Childhood Cancer Survivor Study

## 1. Purpose/Specific Objectives

Childhood cancer survivors are a growing population in the US (currently over 379,000). Unfortunately, these survivors are at risk for adverse health late effects from treatment such as cardiovascular disease and premature mortality. Survivors require lifelong follow-up care to identify, monitor, and treat medical and psychosocial late effects stemming from their cancer, its treatment, and lifestyle factors. However, over 70% of childhood cancer survivors do not obtain specific risk-based follow-up care. Adolescent and young adult (AYA) survivors of pediatric cancers are particularly vulnerable to lapses in follow-up care due to ineffective transitions from parent-guided management to self-management of care.

The transition from parent-guided management to self-management of long-term follow-up care involves assuming primary responsibility for tasks such as managing health records, making appointments, filling and taking prescriptions, and understanding late effects monitoring and cancer screening needs. It occurs during a critical developmental period when AYAs may be unaware or fail to recognize their health risks and need for regular follow-up. Barriers to successful transition include survivors' lack of knowledge of their diagnosis and treatment, cancer-related anxiety and other emotional concerns, and failure or inability to assume personal responsibility for health.

A survivor-focused intervention is likely to have the greatest impact on health outcomes because giving AYA survivors the knowledge, skills, support, and self-efficacy to manage their follow-up care will apply to any setting (i.e., cancer center or community-based primary care). This project takes an innovative approach to improving AYA survivors' self-management of long-term follow-up care through adaptation of an evidence-based problem-solving skills training (PSST) intervention and the addition of peer mentors to facilitate completion of the intervention. PSST has been shown to improve problem-solving skills in other cancer contexts, and we will adapt the content of the program to address the needs of AYA cancer survivors using patient, parent, and provider input. We anticipate that the adapted program will focus on improving disease knowledge, health motivation, problem-solving skills, stress management, and communication with caregivers and providers, all of which are important constructs to promote transition readiness as outlined in the Social-Ecological Model of AYA Readiness for Transition (SMART). Peer mentors have been suggested as an innovative approach to support healthcare transitions, and many AYA survivors express a supportive care need to connect with other young adult survivors and seek advice from others who "get it."

The goal of this project is to develop and evaluate a peer mentoring self-management intervention to improve self-management skills for AYA survivors. We will evaluate feasibility (i.e., enrollment, retention, satisfaction with the program) and preliminary efficacy (i.e., changes in survivors' healthcare self-management skills, readiness to transition, and cancer-related anxiety). In Phase 1, we will use AYA survivor, parent, and provider interviews to adapt an evidence-based problem-solving skills training program to promote AYA self-management of care. We will recruit and train peer mentors to implement the PSST intervention. In Phase 2, we will conduct a pilot test of the program with 40 young adult survivors ages 18-25 years transitioning to self-management of follow-up care. Based on feedback collected in Phase 2, we will refine the online modules and conduct usability testing of the new modules in Phase 3A. We will then evaluate the feasibility and preliminary efficacy of the self-management + peer mentoring intervention in a randomized two-arm trial comparing the intervention to usual care (Phase 3B).

## 1.1 Objectives/Hypotheses

### **Aim 1: Develop the self-management + peer mentoring to improve AYA self-management of long-term follow-up care.**

Qualitative research with AYA cancer survivors, parents, and healthcare providers will be conducted to adapt an evidence-based problem-solving skills training (PSST) program to address the needs of AYA survivors.

### **Aim 2: Evaluate the feasibility of the self-management + peer mentoring program.**

We will examine feasibility through study enrollment rates, retention rates, adherence to the intervention, reasons for study drop out, and patient and mentor satisfaction with the program.

*Hypothesis 1:* Based on literature, we expect enrollment >50% of eligible patients and retention >80%.

*Hypothesis 2:* We expect patients enrolled in the mentor program to complete >75% of intervention sessions

### **Aim 3: Assess preliminary outcomes of the peer mentoring program.**

*Hypothesis 3 (Phase 2):* Participants in the mentor group will demonstrate improvement in self-management skills, transition readiness, and anxiety.

*Hypothesis 4 (Phase 3):* Participants in the self-management + peer mentor intervention will demonstrate greater improvement in transition readiness than participants in the usual care group.

*Hypothesis 5 (Phase 3):* Participants in the self-management + peer mentor intervention will participate in survivorship and preventive healthcare at greater rate than participants in the usual care group.

## 2. Background and Significance

### **The transition to adult self-management of health care is often ineffectively managed by AYAs.**

Ineffective transition to adult self-management of care results in inadequate follow-up care and potential health problems. Although it is recommended that childhood cancer survivors obtain long-term follow-up care tailored to address the risks of their cancer, treatment, and lifestyle (called “risk-based follow-up care”), over 70% of young adult childhood cancer survivors do not obtain such care. Results from the largest cohort study of childhood cancer survivors, the Childhood Cancer Survivor Study (CCSS), show that even survivors at greatest risk for late effects demonstrate low rates of cancer screening. The transition to adulthood is a particularly challenging time when many AYAs are lost to follow-up. This is both a personal medical risk because late effects may go undetected or be misdiagnosed or mistreated, and a societal risk because lack of monitoring can lead to increased healthcare utilization and costs that may have been preventable. Barriers to adult-oriented health care transition for AYA survivors

## Promoting Follow-Up Care Self-Management for Adolescent and Young Adult (AYA) Childhood Cancer Survivors

[name], MPH

include survivor-related factors, such as inadequate knowledge of their cancer history and treatment, complex medical conditions, anxiety, and difficulty assuming personal responsibility for health. These survivor-related factors call for a survivor-focused intervention.

### Theoretically-driven interventions to improve self-management of care are needed.

Although there is attention to AYA transition in the literature, a lack of transition-related theoretical frameworks has hindered the development and evaluation of targeted interventions to promote self-management of care. The Social-Ecological Model of AYA Readiness for Transition (SMART) proposes that there are modifiable factors that interact to promote AYA readiness for transition (Figure 1). Transition readiness refers to the capacity of the AYA and his/her support network to prepare for and complete the process of moving to adult-oriented care. Factors related to transition readiness include knowledge of health history, risks, and needs; self-management skills and self-efficacy for managing care; beliefs and expectations regarding the transition process or adult-oriented care (such as belief that adult provider will not understand patient's needs); goals related to health transition; relationships with parents and providers; and psychosocial functioning of patients, parents, and providers (such as anxiety about the transition process or future health). Problem-solving skills training (PSST) is a generic, cognitive-behavioral intervention that can be readily adapted to target these constructs. For example, PSST can be used to help AYAs set transition and self-management goals, explore beliefs/expectations related to the goals or barriers to such goals, manage stress, and promote self-efficacy by breaking down large goals into small, achievable steps. We chose PSST as an intervention because it empowers individuals to improve self-management skills, which include maintaining health records, making appointments, filling and taking prescriptions, and understanding health risks and monitoring needs. PSST also has a strong evidence base and has been shown to be effective for increasing problem-solving skills for parents who are managing a child's cancer treatment. We will use Phase 1 of this project to explore strategies for adapting PSST to address many of the modifiable components of the SMART model, including knowledge and communication with parents and providers.

### Peer mentoring meets a unique need for AYA childhood cancer survivors.

Qualitative and quantitative studies suggest that AYA survivors want to discuss their medical care needs with other AYA survivors. Although peer mentoring has been recommended as an innovative approach to facilitate health care transitions for AYAs, the only published intervention utilizing this approach for survivors is a peer-delivered counseling intervention for smoking cessation among adult childhood cancer survivors from the CCSS. Childhood cancer survivors who received the peer-delivered telephone counseling intervention were twice as likely

[figure not shown]

Figure 1. SMART model

to quit smoking as survivors who received the self-help print intervention, providing evidence of effectiveness of peer-to-peer programs for health behavior change in this population.

**Peer mentoring programs delivered using technology can be implemented across a variety of settings.**

The Adolescent and Young Adult Oncology Progress Review Group (AYAO PRG) recommended the development of standardized peer-to-peer programs as a strategy for supporting the psychosocial needs of AYA cancer patients and survivors. The AYAO PRG suggested that efficacious programs be disseminated by partnering with cancer centers, oncology professional societies, and community-based support groups that work with AYA survivors. By partnering with various organizations, peer mentoring programs can be initiated and maintained with minimal health care system support. Peer-to-peer programs are also likely to be relatively low cost, as demonstrated by the peer counseling smoking cessation intervention for childhood cancer survivors, which has recently been translated to a web-based intervention. The use of technology to deliver skills-building modules and peer mentoring aligns with AYAs' preferences for technology, with 85% of young adults 18-29 owning smartphones. It also sets up the program for dissemination. Finally, since many childhood cancer survivors participate in volunteer activities and informal peer-to-peer outreach is commonly offered to cancer patients, sustaining a peer-to-peer program on a large scale is plausible.

### **3. Research Design and Methods**

This research will be conducted in three phases. In Phase 1, we will use provider, survivor, and caregiver interviews to adapt PSST to focus on AYA self-management of care and develop the intervention. In Phase 2, we will conduct a single arm pilot test of the program with 40 young adult survivors ages 18-25 years and 20 peer mentors. Based on feedback collected in Phase 2, we will refine the online modules and conduct usability testing of the new modules in Phase 3A. We will then evaluate the feasibility and preliminary efficacy of the self-management + peer mentoring intervention in a randomized two-arm trial comparing the intervention to usual care (Phase 3B). The biostatistician will determine a randomization scheme using an undisclosed block size. The scheme will be uploaded to DatStat for automatic assignments. For a backup, randomization assignments will be provided to PI in sealed envelopes as well.

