#### **3.5.4 Consent Procedures**

Phase 1 and 2: The study will be explained to the potential participant by the Principal Investigator or trained study staff via phone. The PI or study staff will review essential elements of consent and answer any questions. Interested and eligible participants will be emailed a link to an online consent form prior to starting the program. To consent, potential participants will be instructed to click "submit the form" button in order to consent.

Phase 3A: The study will be explained to the potential participant by the Principal Investigator or trained study staff in person or on the phone. All subjects will receive a

copy (paper or electronic) of the consent form. To document the process of the consent, we will complete “documentation of Consent Process” form to document that 1) study subjects were provided with a copy of the Consent Forms, 2) all essential elements of informed consent were discussed with subjects, 3) subjects were given adequate time to read and discuss the study with study staff, and 4) all questions asked by the subjects about the study were answered.

Phase 3B: As done in Phase 2, the study will be explained to the potential participant by the Principal Investigator or trained study staff via phone. The PI or study staff will review essential elements of consent and answer any questions. Interested and eligible participants will be emailed a link to an online consent form prior to starting the program. To consent, potential participants will be instructed to click “submit the form” button in order to consent. Since consent forms will be completed online, we are requesting a waiver of documentation of consent.

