**Peer Mentor Training.** Peer mentors will attend a one-day training workshop conducted by the PI and study staff (similar to other peer mentor programs). Peer mentors will be given the Peer Mentor Handbook, a manual adapted from the National Mentoring Research Center, which details their roles, responsibilities, and an outline for each mentor call. Presentations, interactive discussions, and role plays will be used to teach mentors how to facilitate their mentee's use of the online self-management modules, and how to provide informational and emotional support to their mentees. Ethical issues, including confidentiality and setting boundaries with peers, will be discussed. Peer mentors will also be instructed in how to securely transfer audio recordings of their calls with mentees and destroy the original file from their devices. In addition to the in-person training, we will email these instructions. Peer mentors will have regular weekly phone supervision with the PI or trained study staff once assigned mentees to review mentoring calls and discuss any challenges experienced. During this supervision call, the PI or research staff will verbally confirm that peer mentors have destroyed any transferred audio recordings for the study.

**Phase 3B: Self-Management + Peer Mentoring Intervention.** The intervention content is the same as described in Phase 2. There are a few minor differences: (1) the online modules will be hosted on its own website instead of Canvas; this website will be built in Phase 3A using Radian Creative Group, LLC, an experienced technology development firm that has a strong history of collaboration with [name] and other Rutgers Cancer Institute of New Jersey investigators; (2) TigerText is now called TigerConnect and has expanded its services to include secure videoconferencing; therefore, doxy.me will no longer be used; and (3) peer mentor training can be completed either in-person or via videoconference to minimize peer mentor burden.

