**Phase 3B: Usual Care Comparison.** The Usual Care group will complete surveys only. To select an appropriate comparison, we reviewed the literature of advantages/disadvantages of different designs. This study can be characterized as a phase IIb feasibility pilot focused on feasibility and acceptability, as well as detecting a clinically significant signal over noise. A usual care comparison group is recommended for initial evaluations of such interventions, as it maximizes statistical power and protects against falsely concluding that the intervention lacks efficacy. We will offer access to the online educational modules upon completion of all study procedures to the interested subjects in the usual care comparison group.

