## Promoting Follow-Up Care Self-Management for Adolescent and Young Adult (AYA) Childhood Cancer Survivors

[name], MPH

Phase 3A & 3B: This study is minimal risk. The PI will convene a Data and Safety Monitoring Board (DSMB) composed of the biostatistician and a behavioral scientist and clinician who are not associated with the study. The committee will be responsible for oversight of patient safety and will meet yearly to review patient safety and trial progress. This review will include for each arm of the study: the number of patients enrolled, withdrawals, serious adverse events both expected and unexpected, and responses observed. All unexpected and/or serious adverse events (AEs) occurring during the active portion of the intervention or up to 30 days after the last peer mentor call, will be reported to the Rutgers Cancer Institute of New Jersey Office of Human Research Services and the Rutgers Biomedical Sciences Institutional Review Board (IRB) in accordance with IRB policy. The PI and study staff will continuously monitor for any potential AEs. Peer mentors will be instructed in how to assess and report adverse events during the mentor training and study staff will explicitly ask about adverse events during regular supervision sessions with each mentor. The research team will review and discuss via a teleconference any serious adverse events to ensure protections to the participants and security of the data, and discuss any modifications needed. If modifications are needed, they will be implemented immediately following standard IRB procedures. The Rutgers Cancer Institute of New Jersey Scientific Review Board and the IRB will review this Data and Safety Monitoring Plan and the study protocol prior to initiation of the study. A report with recommendations from the DSMB will be submitted annually to the IRB with the continuing review for the study.

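### Phase 3B randomisation relies on one undisclosed block size in an open trial; randomly varying sizes would remove most allocations that can be predicted with certainty, at almost no cost

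*Combined protocol and SAP*

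**What the plan says.** Sequence generation is described only in section 3 (Research Design and Methods): "The biostatistician will determine a randomization scheme using an undisclosed block size". The size is in the singular. Varying sizes, strata and the allocation ratio are not mentioned. Delivery is central: "The scheme will be uploaded to DatStat for automatic assignments". There is also a paper copy: "For a backup, randomization assignments will be provided to PI in sealed envelopes as well".

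Four other places show who can see what in Phase 3B:

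- **Enrolment.** Section 3.5.4 (Consent Procedures): "As done in Phase 2, the study will be explained to the potential participant by the Principal Investigator or trained study staff via phone".
- **Knowledge of assignments.** Section 4.1 (Peer Mentor Training): "Peer mentors will have regular weekly phone supervision with the PI or trained study staff once assigned mentees". This sits in the Phase 2 description, and section 4.1 carries the intervention content into Phase 3B with minor differences.
- **Confirmation for Phase 3B.** Section 6 (Data and Safety Monitoring): "study staff will explicitly ask about adverse events during regular supervision sessions with each mentor".
- **Openness.** Section 4.1 (Usual Care Comparison): "The Usual Care group will complete surveys only". No blinding is described.

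**The concern.** With permuted blocks, past assignments predict coming ones. In a two-arm trial, knowing who has a mentor also shows who does not. If all blocks have the same size and there is a single list, the arm totals are equal at every multiple of that size. Someone who follows the assignments in order can therefore work the size out, and withholding it is only partial protection.

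Someone who knows or suspects the next assignment can, even without meaning to, influence when a more motivated survivor is enrolled. Motivation could plausibly affect the self-reported RTQ score. With about 25 per arm, a few such enrolments could shift the comparison. This predictability comes from the scheme itself and is separate from the question of who holds the backup envelopes.

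**Working it through.** **Inputs.** N = 50 (section 3.3). SD 0.83, two-sided alpha 0.05, 80% power and a detectable difference of 0.66 (section 3.3, text after Table 1). The block size B is not given, so a range is shown. The 1:1 ratio is an assumption.

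**Check of the 1:1 assumption.** The plan gives no figure on predictability, but its detectable difference can be reproduced with 25 per arm:

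(1.960 + 0.842) × 0.83 × √(2/25) = 0.658, or 0.66 as stated.

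The noncentral t gives 0.671. Equal allocation therefore fits the plan's own figure.

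**Step 1: fixed size, known to the observer.** An allocation is certain once one arm has used its B/2 places in the block. The expected certain share of a complete block is 1/(B/2 + 1), so the expected number per block is B/(B/2 + 1). For B = 4, 6 or 8, a remainder of 2 participants is left after the complete blocks. The first two places of such a block are never certain, so the remainder adds nothing.

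| B | Certain per block | Complete blocks in 50 | Certain of 50 | Share |
|---|---|---|---|---|
| 2 | 1.00 | 25 | 25.0 | 50% |
| 4 | 1.33 | 12 | 16.0 | 32% |
| 6 | 1.50 | 8 | 12.0 | 24% |
| 8 | 1.60 | 6 | 9.6 | 19% |
| 10 | 1.67 | 5 | 8.3 | 17% |

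Simulation agrees with these shares.

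**Step 2: fixed size, to be learned.** Step 1 gives the observer the size from the first participant. For a fair comparison with mixed sizes, the observer should know only a set of candidate sizes and rule them out as assignments appear. A prediction counts as certain only if every candidate still possible agrees. Simulating 4,000 sequences of 50 per case gives:

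- Candidates 4 and 6: about 22% certain, whichever is used. If the size is 4, the median time to identify it is 18 allocations, and in about 20% of sequences it is never identified.
- Candidates 4, 6 and 8: about 11% if the size is 4, and about 17% if it is 6 or 8. Blocks of 4 can never be strictly distinguished from blocks of 8, because every run of balanced fours also fits blocks of 8.

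**Step 3: randomly mixed sizes, set known.** Every block state consistent with the history is tracked. Mixing 4 and 6 leaves about 2.8 of 50 certain (6%). Mixing 4, 6 and 8 leaves about 1.2 of 50 (2%).

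**Step 4: best guess.** The success rate of always guessing the more likely arm is 70% for a fixed 4, 68% for a fixed 6 and 66% for a fixed 8. It is 69% for mixed 4/6 and 68% for mixed 4/6/8. Mixing lowers it slightly relative to a fixed 4 and not at all relative to a fixed 6 or 8.

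**The case against.** The case on the other side has five parts.

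1. **The wording is thin evidence.** The sentence neither states nor excludes varying sizes. A reader might infer that the plan commits to one fixed size. That is the natural reading of a singular noun, but it is not stated outright. This stands, and if sizes already vary the sponsor need only say so.
2. **A reader might infer that up to a third of allocations are exposed.** The documents do not support that as a bound. It is the average for a block of 4 under 1:1. A block of 2 gives half, a block of 10 a sixth, and no size is documented. When the size must first be learned, the figures fall to those in Step 2. This stands, but a clear gain from mixing remains.
3. **There are safeguards.** DatStat assigns automatically and the size is withheld. Registry staff, not study staff, make first contact with registry patients (section 3.5.3), although clinic recruitment is also allowed. Participants submit consent online themselves, and eligibility uses RTQ thresholds. These limit timing and steering without excluding them, since none of them hides past assignments. Prediction still needs someone to follow both arms in order.
4. **The overlap is of roles.** A reader might infer that the same individuals enrol and supervise. The documents show shared role labels only. They also describe no separation between the two functions.
5. **The consequence is limited.** The sample size rests on feasibility, whose acceptance and retention rules use the whole sample. Efficacy is preliminary, and the RTQ model tests a time-by-treatment interaction with baseline measured. This stands and keeps the point minor.

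**Conclusion.** The point holds as a low-cost improvement. If one fixed size is used, about 17% to 50% of the 50 allocations are certain to an observer who knows it, depending on a size between 10 and 2. On the like-for-like basis, where the size must be learned, the figure is about 22% against 6% with mixing (sizes 4 and 6), or 11% to 17% against 2% (sizes 4, 6 and 8).

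This rests on 1:1 allocation, one unstratified list, a single fixed size, and enrolling staff who see past assignments in order. The ratio is not stated, and the other three are readings of the text.

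A reader might go further and infer that the RTQ comparison is biased, or that staff would steer enrolment. Nothing in the documents shows either, and no size of bias can be derived from them. The supported statement is that predictability could bias the RTQ comparison, which is secondary to feasibility. The feasibility rules compare no arms and are not affected.

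**What to change.** In section 3, replace the reference to an undisclosed block size with randomly permuted blocks of randomly varying size, the sizes being known only to the biostatistician. If the sizes already vary, the sentence should simply say so.

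The cost is regenerating one list before it is uploaded to DatStat, and possibly one or two more participants of imbalance between arms at the end.

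The change removes most certain predictions. It does not stop educated guessing, and it does nothing about the backup envelopes held by the PI. Keeping past assignments and the envelopes away from those who enrol would be a useful addition.
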